## I. Background and objectives of research: foreign and domestic research status, preliminary research foundation and design basis of research etc.

Uterine fibroids are benign tumors from smooth muscle cells of the uterus. The pathophysiological principle of fibroids is not clear yet. Genetic predisposition, exposure to steroid hormones, and growth factors can promote formation and growth of fibroids. Uterine fibroids are common among women aged between 35 and 50. Nearly half of reproductive-age women suffer from uterine fibroids. The morbidity of uterine fibroids has been stubbornly high for years and increases year by year. The most common symptoms are menorrhagia and pressure symptoms, such as hypogastralgia, frequent urination and difficult defecation. Hysterectomy is the one and only radical treatment that can completely avoid recurrence of uterine fibroids. However, more and more women expect to avoid hypogastralgia, for they would like to choose an operation that can reserve their uterus in spite of their will of pregnancy. Though there are many surgical options for uterine fibroids, each option has certain risks and a possibility of reoperation caused by recurrence (which increases over time with symptoms). In addition, some rare types of uterine fibroids, including intravenous leiomyomatosis, leiomyomatosis peritonealis disseminate and benign metastasising leiomyomas, are intractable, for the scope of relevant surgery is large and sometimes a single operation cannot affect a radical cure. Hence, it is urgent to explore a treatment that can preserve fertility.

It's no accident that many women are not willing to undergo surgery because of surgical risks, a possibility of recurrence and postoperative residual fibroids. Therefore, there's a large demand of effective drugs for long-term treatment of uterine fibroids that can replace surgery in medical treatment. Traditionally, it is believed that uterine fibroids are ovarian-hormone-dependent benign tumors, and main drugs for uterine fibroids include GnRH-a, progestin receptor antagonist and combined oral contraceptive etc. These drugs are mainly used to shrink fibroids, inhibit growth of fibroids and prevent deterioration of the disease. However, though there are many medicines for uterine fibroids, their curative effects are of great difference. After drug withdrawal, the disease is easy to recur and many of these medicines can cause numerous adverse effects, leading to short-term administration only. Thus, it is urgent to find a new well-tolerated drug with a lasting effect for uterine fibroids.

mTOR is a type of conservative serine-threonine kinases regulating the process of protein synthesis through multiple target molecules in terms of transcription and translation, promoting and coordinating cell growth and proliferation. Research showed that 24-hour treatment of primary smooth muscle cells with rapamycin can cause irreversible growth arrest. An *in vivo* study showed that to inhibit mTOR of female Eker rats with WAY-129327, analogue of rapamycin, could significantly reduce incidence, multiplicity and sizes of tumors. Fritsch et al. designed a nude mouse model of patient-derived tumor xenografts (PDX) (which retains histologic and functional characteristics) and first proved that rapamycin could inhibit growth of PDX effectively with an *in vivo* model. As the mTOR pathway is a type of tumor target molecules of high specificity and specificity in tissue of uterine fibroids, it can be used as a target molecule of intervention treatment, providing a new idea for non-surgical treatment of uterine fibroids. Hence, the application of mTOR inhibitors can offer a new therapy for women with related symptoms of uterine fibroids.

Evidence has shown that LAM does not originate from lungs but migrates to lungs through lymph vessels or blood. Lot of research showed that LAM might be variants outside the uterus rooting in

uterine smooth muscle cells. Food and Drug Administration (FDA) approved the application of rapamycin to treatment of moderate-severe LAM. Results of its clinical application showed that mTOR inhibitors brought landmark change to LAM patients. Before mTOR inhibitors were applied for treatment of LAM, lung transplantation was almost the only therapy for LAM. At present, application of mTOR inhibitors is the main clinical therapy for LAM with significant effects and high safety. Hence, the prospect of application of mTOR inhibitors to treatment of uterine fibroids is promising, especially for patients with symptomatic uterine fibroids or myomatosis who refuse or are not suitable for operative treatment. Thus, treatment with mTOR inhibitors may become the best long-term therapeutic schedule that can replace operative treatment for patients with uterine fibroids.

mTOR inhibitor rapamycin (sirolimus), is a new type of macrolide immunosuppressors. Initially, sirolimus was used as low-toxicity antifungal antibiotics. In 1978, it was found that it could realize immunosuppression of autoimmune diseases. In 1989, it was on trial as a new type of immunosuppressors against rejection of organ transplantation. In September, 1999, FDA formally approved its appearance on the market. So far, more than twenty countries have approved or registered it for prevention of acute rejection of patients receiving organ transplantation. Currently, there are 2082 clinical trials relating to rapamycin and 924 of them have been finished. In China, as a new drug of the second category, sirolimus was permitted to be used clinically in 2002. With 15-year clinical application, its safety data also show its favorable safety features without related security problems.

However, there's no application of mTOR inhibitor sirolimus to treatment of uterine fibroids yet and its curative effects and safety still need to be verified through rigorous clinical trials. Therefore, this study used sirolimus to treat patients with symptomatic uterine fibroids or myomatosis who refused or were not suitable for operative treatment, discussed its therapeutic value for uterine fibroids or myomatosis and provided a clinical basis for formulation of the best therapeutic schedule of non-surgical treatment for uterine fibroids or myomatosis.

## II. Research objectives

1. Evaluation of curative effects of sirolimus on symptomatic and recurrent uterine fibroids and/or various rare types of myomatosis
2. 1.Evaluation of safety of sirolimus in treatment of symptomatic and recurrent uterine fibroids and/or various rare types of myomatosis

## III. Research content

1. Symptom control rates after medication for 3 and 6 months
2. Recurrence rates of symptoms after 12 months of drug withdrawal
3. Evaluation of safety and side effects of the drug

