## IV. Research design

1. This study is a non-random open-label clinic trial carried out by the department of gynaecology and obstetrics, Peking Union Medical College Hospital.
2. All patients who accorded with inclusion criteria and signed informed consents received sirolimus treatment for at least three months. After drug withdrawal, there patients were followed up for at least one year.
3. There should be at least 25 patients included in this study without an upper limit of included patients.

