## VI. Therapeutic schedule

1. Initial dosage of administration and dosage regimen: take 2mg of sirolimus once a day since the fifth to seventh day of menstruation. After one week of medicine taking, subjects are called for an interview. If a subject has severe adverse reactions and fails to tolerate the drug, her weekly dosage can be reduced to 0.5mg, where the minimum daily dosage should be 1mg / day. If the subject still fails to tolerate the drug, she should quit; if she feel unwell but tolerable, the administration should be continued for another three months. After the three months, evaluate the condition of this subject.
2. Subsequent dosage of administration and dosage regimen: if the condition of a subject is significantly improved after taking 2mg of sirolimus once a day for three months, the initial administration should be continued. If the condition of a subject shows no significant improvement, the dosage should be changed into 2.5mg-3mg once a day. If this subject fails to tolerate the dosage, she should quit this study; if she can tolerate the dosage, this dosage regimen should be executed for three months. After that, her condition should be evaluated again.
3. Iron supplement: if hemoglobin of a subject  $\leq 10.9$  g/dL, she should receive iron supplement in accordance with the standard dosage regimen. However, the iron supplement is not regarded as a part of treatment of this study and will be recorded as a part of drug combination.
4. If the condition of a patient with a rare type of uterine fibroids (including intravenous leiomyomatosis, leiomyomatosis peritonealis disseminate and benign metastasising leiomyomas) is under control with a tolerable drug, the patient can continue this drug therapy after this six-month study.

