### 3. Evaluation after treatment

Evaluation of curative effects and safety is conducted at the end of the drug therapy, six and twelve months after the treatment, where the evaluation content is the same as that before the trail.

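### The 12-month recurrence rate cannot by itself show how many treated women keep a lasting benefit, and it may miss women who relapse by month 6 and then leave

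*Combined protocol and SAP*

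**What the plan says.** The protocol and analysis plan are one document. Section III lists two efficacy outcomes. Item 1 is "Symptom control rates after medication for 3 and 6 months". Item 2 is "Recurrence rates of symptoms after 12 months of drug withdrawal". Neither control nor recurrence is defined, and item 2 names no denominator.

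Section IV, item 2 describes who is treated: "All patients who accorded with inclusion criteria and signed informed consents received sirolimus treatment for at least three months". It then describes the off-drug period: "After drug withdrawal, there patients were followed up for at least one year". Item 3 sets the size: "There should be at least 25 patients included in this study without an upper limit of included patients".

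Section VIII.3 schedules evaluations at the end of drug therapy and "six and twelve months after the treatment", so there are two off-drug visits.

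Two items in Section VI bear on who can contribute to a recurrence rate. Item 2 keeps unimproved women in the study: "If the condition of a subject shows no significant improvement, the dosage should be changed". Under item 4, when a woman with a rare fibroid type is under control and tolerates the drug, "the patient can continue this drug therapy after this six-month study".

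Section IX gives descriptive summaries and a 0.05 significance level. Its efficacy paragraph covers quality of life, fibroid control and symptom improvement. It does not mention recurrence.

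**The concern.** Lasting effect after withdrawal is the stated reason for seeking a new drug (Section I), and item 2 of Section III is the only outcome that addresses it. That outcome falls short in three ways.

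- **It is conditional on response.** A woman has to be controlled before she can recur. A drug that controls few women can show the same recurrence rate as one that controls many, so the rate alone does not say what share of treated women gain lasting benefit.
- **It is tied to one time point.** If the rate is computed on women evaluated at month 12, a woman who relapsed by month 6 and then left (for other treatment, say) falls out of both numerator and denominator. Such losses make the drug look more durable than it was.
- **Two foreseeable groups have no stated place.** Unimproved women who remain in the study can reach the off-drug year without ever having been controlled. Controlled women with rare types who stay on the drug may have no withdrawal date at all.

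The trial has no comparator, so these rates are most of the efficacy evidence. A reader could take a recurrence percentage as a measure of lasting success when it is not one.

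**Working it through.** **Inputs.** The documents give one number that can be used, the minimum of 25 patients (Section IV, item 3). They give no derivation of it, and no expected control rate, recurrence rate or dropout rate, so there is no figure of the plan's own to reproduce. The counts below are assumptions chosen to show how the quantities behave.

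Let N = women treated, C = women controlled at the end of therapy, R = controlled women whose symptoms return by month 12. For the first step, assume that all controlled women stop the drug and are seen at both off-drug visits.

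**Step 1: recurrence against durable control.**

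- Recurrence among controlled women = R/C
- Durable control over all treated = (C − R)/N

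| Controlled C | Recurring R | Recurrence R/C | Durable control (C − R)/25 | Exact 95% interval for durable control |
|---|---|---|---|---|
| 10 | 6 | 60% | 4/25 = 16% | 5% to 36% |
| 15 | 9 | 60% | 6/25 = 24% | 9% to 45% |
| 20 | 12 | 60% | 8/25 = 32% | 15% to 54% |

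The recurrence rate is the same in every row, while durable control doubles from the first row to the last. Intervals are Clopper-Pearson. For 9/15 the exact 95% interval is 32% to 84%, so the conditional rate is also imprecise at this size.

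**Step 2: relapse by month 6, then leaving.** Take the middle row (C = 15, R = 9). Suppose k of the 9 relapsed by the month-6 visit and left before month 12, and everyone else was seen. A rate computed only on women seen at month 12 is (9 − k)/(15 − k):

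- k = 0: 9/15 = 60%
- k = 1: 8/14 = 57%
- k = 3: 6/12 = 50%

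A cumulative count using both visits stays at 9/15 = 60% in each case. The month-6 evaluation needed for this is already scheduled.

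**Step 3: women who stay on the drug.** Suppose m controlled women with rare types continue the drug. They have no off-drug month-12 state, so they cannot enter R/C, and C must be replaced by C − m in that rate. In the all-treated figure they are neither durably controlled off drug nor failures. With D women durably controlled off drug, the figure is D/N with them in the denominator and D/(N − m) without. The two differ whenever m and D are above zero, so the report should show both.

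Section IV, item 2 sends the treated patients into at least a year of follow-up after withdrawal. Section VI, item 4 describes patients who do not withdraw. The two statements must be reconciled before the number at risk can be fixed.

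**The case against.** The strongest reply is that recurrence presupposes control. Item 2 of Section III follows directly after the control rates, so its denominator is clear enough. Following every woman off drug serves safety as well and does not make every woman part of the recurrence denominator. That stands.

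A reader might infer more: that the plan's own wording puts all treated women in the denominator. On the assumed counts of 15 controlled and 9 recurring, the same data could then be reported as 9/25 = 36%, 9/15 = 60% or 19/25 = 76%. The documents do not support this. The first figure counts never-controlled women as free of recurrence, and the last counts them as recurrences. Both are strained readings of the word, and all three rest on counts that appear nowhere in the plan. Nor is it true that every treated woman is followed off drug, given the rare-type exception in Section VI, item 4.

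A second reply is that durable control can be derived from the two listed rates: 15/25 × (1 − 9/15) = 15/25 × 6/15 = 24%. That works when control is judged at the end of therapy, every controlled woman stops the drug, and nobody is lost. Item 1 of Section III measures control at 3 and 6 months, Sections V and VI provide for women who quit, and some women may stay on the drug. The product cannot be relied on under those conditions.

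Third, no text says that a woman lost between months 6 and 12 is dropped. That is fair. It is a risk left open by a rate set only at month 12, not a stated rule.

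Finally, the analysis is descriptive, with no hypothesis test or success threshold. This lowers the severity.

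**Conclusion.** The point holds as a better analysis that the plan should adopt. Because the rate in Section III, item 2 is conditional on response, it cannot show how many treated women gain lasting benefit. Because it is set only at month 12, it can lose relapses already seen at month 6. Two groups described in Section VI have no stated place in it.

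On the assumed counts, one recurrence rate of 60% is compatible with durable control of 16% to 32% of 25 treated women. One to three early relapses lost before month 12 would lower the reported rate from 60% to between 57% and 50%. These sizes illustrate the problem and are not predictions. The first gap closes only if the share controlled at end of therapy is reported alongside, with complete off-drug follow-up. The second disappears if nobody leaves after an early relapse.

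It should be corrected before analysis but does not undermine the trial, since nothing in the plan turns on a threshold for this rate.

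**What to change.** Revise Section III, item 2, and add matching text to Section IX.2, so that two figures are reported.

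(a) **Cumulative recurrence.** Among women controlled at the end-of-therapy evaluation who stop the drug, report the proportion whose symptoms have returned by month 6 and by month 12, using both visits and giving the number at risk at each. Simple counts or a life table will do. A recurrence seen at month 6 counts even if month 12 is missing.

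(b) **Durable control.** Report women controlled at the end of therapy and still controlled at month 12 off drug, over all treated women, with an exact 95% interval. Women never controlled count as not durably controlled. Women who continue the drug form a separate, stated category, and the figure is given with and without them in the denominator.

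Apply one written symptom criterion at the end of therapy, month 6 and month 12. Reconcile Section IV, item 2 with Section VI, item 4 on who withdraws.

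The cost is some protocol and analysis wording and one extra table line. No new visits are needed. However, the off-drug evaluations repeat the pre-trial list in Section VIII.1, which includes history but no named symptom measure, so the symptom status used for (a) and (b) must actually be recorded there. The downside is that the recurrence rate rests on fewer women and has a wider interval.

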## IV. Research design

1. This study is a non-random open-label clinic trial carried out by the department of gynaecology and obstetrics, Peking Union Medical College Hospital.
2. All patients who accorded with inclusion criteria and signed informed consents received sirolimus treatment for at least three months. After drug withdrawal, there patients were followed up for at least one year.
3. There should be at least 25 patients included in this study without an upper limit of included patients.

## V. Selection of subjects

### A. Inclusion criteria

1. Patients who suffer from menorrhagia and pressure symptoms and whose pelvic ultrasound or pelvic MRI indicates uterine fibroids; or who has underwent myomectomy but suffer from menorrhagia and pressure symptoms again with pelvic ultrasound or pelvic MRI indicating uterine fibroids; or whose other imageological examinations or established surgical diagnosis indicate various rare types of myomatosis and who expect a drug therapy.
2. Symptoms of uterine fibroids can be confirmed if one or multiple symptoms below exist:
  - 1) . MP shows an excessive amount of bleeding during menstruation ( $>80.0$  mL)
  - 2) . A subject report shows three excessive amounts of bleeding during menstruation in latest six months

3) .A subject report indicates pelvic pressure symptoms/pain that are likely related to uterine fibroids.

3. According to results of medical history, physical examinations, gynecological examinations and laboratory examinations, patients are in a good overall condition (except uterine fibroids).

4. Cervical smears show a normal result or have no clinical significance, where further follow-up is unnecessary. If there's a normal result in the latest six month in the medical record of a subject, the subject can pass the inspection of cervical smears. A HPV test can be applied to subjects with equivocal ASCUS as an auxiliary test. ASCUS subjects who get a negative result of a HPV test can be included into this study.

5. Endometrial biopsy should be conducted to eliminate non-endometrial lesions if necessary.

6. Subjects didn't receive any drug therapy for uterine fibroids three months before the clinical test.

7. Female adults have menstruation (>18 years old) and are not during pregnancy and lactation.

8. Subjects have good organ function and results of their biochemical examinations meet the following conditions:  $AST \leq 2.5 \times$  the upper limit of normal (ULN),  $ALT \leq 2.5 \times$  the upper limit of normal (ULN), Serum total bilirubin  $\leq 1.5 \times$  the upper limit of normal (ULN), Creatinine  $\leq 1.5 \times$  the upper limit of normal (ULN)

9. Patients have signed the informed consent.

#### B. Exclusion criteria

1. Patients are in a period of pregnancy and lactation (patients delivered, miscarried or breast-feed in three months before the treatment)

2. Patients are allergic to any ingredient of the medicine

3. Patients suffer from a disease requiring immediate blood transfusion

4. Patients suffer from a disease that may impact implementation of the study or explanation of results. This type of diseases includes:

1) Known severe blood coagulation disorders

2) Known anemia that is not caused by HMB

3) Known hemoglobinopathy

4) Patients suffered or suffer from cancer of the uterus, cervical carcinoma, ovarian cancer or breast cancer

5) An ultrasonic examination shows one or multiple ovarian cysts with a diameter  $>30$  mm

6) Ovarian tumors or pelvic mass of unknown origin

7) Known or suspected endometrial polyp  $>15$  mm

5. Alcohol or drug (such as aperient) abuse

6. Undiagnosed abnormal bleeding of the reproductive system.

7. Patients also participate in another clinical medicine study

8. Patients took part in another clinical trial that may influence this study before this study

#### C. Exit criteria

1. A subject suffers from an anaphylactic reaction

2. A patient asks to quit the study because of one's own will or the request of her legal representative. A subject can refuse to follow a further step of this study at any time during the study without a reason. Consequently, the subject won't be affected negatively.

3. A subject is asked to quit this study in some condition (such as obvious poor compliance and security problems)

4. Other conditions leading to termination of this study. For example, researchers think the

continuation of this study may impair health of subjects.

[figure not shown]
#### D. Rejection criteria

1. A subject violates the requirement of the test scheme
2. Data recorded by a patient are of poor quality and incomplete and inaccurate.

[figure not shown]

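### Patients can be rejected or quit after entry and the visible text sets no denominator, so the 3- and 6-month symptom control rates can become completer-type rates

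*Combined protocol and SAP*

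**What the plan says.** All references are to the combined protocol and SAP.

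- **The rates.** The first item of section III is "Symptom control rates after medication for 3 and 6 months". Section IV describes an open-label, non-randomised study with a minimum of 25 patients and treatment for three months or longer.
- **Rejection.** V.D gives two grounds: "A subject violates the requirement of the test scheme" and "Data recorded by a patient are of poor quality and incomplete and inaccurate". Both concern conduct or data that arise only once a patient is in the study.
- **Exit.** V.C allows withdrawal at will and lets a patient be asked to leave, "such as obvious poor compliance and security problems". VI item 1, on the initial dosage, adds: "If the subject still fails to tolerate the drug, she should quit".
- **Exit after month 3.** VI item 2 says "If the condition of a subject shows no significant improvement, the dosage should be changed", and for that group, "If this subject fails to tolerate the dosage, she should quit this study".
- **Visits.** VIII.2 places the month-3 and month-6 efficacy assessments under evaluation during treatment. VIII.3 sets later ones at the end of drug therapy and six and twelve months after treatment.
- **Analysis.** IX.1 calls for case numbers and percentages. IX.2 analyses follow-up and re-examination results. Neither names an analysis set, a denominator, or how rejected, withdrawn or unassessed patients count.

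**The concern.** There is no control arm, so the observed percentage carries the efficacy message. If patients who are rejected or quit drop out of both numerator and denominator, that percentage describes those who stayed, complied and kept good records.

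The 6-month rate is the more exposed. The changed-dosage exit in VI item 2 can reach only patients without significant improvement at month 3, and a patient who takes it has no scheduled month-6 assessment. Rejection is also a judgement made in an open-label study, and nothing visible says it is made without sight of the outcome.

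**Working it through.** **Inputs.** The minimum N = 25 is from section IV. The documents give no expected control rate, rejection rate or dropout, so every other count below is an assumption. The plan has no figure of its own for this point to reproduce.

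**Step 1: the schedule.** A patient who stops in month 4, if followed, is evaluated at the end of drug (month 4) and at 4 + 6 = 10 and 4 + 12 = 16 months. None of these is month 6.

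**Step 2: the formulas.** Let r be the number removed, pc the control rate in those kept and pq the control rate in those removed.

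- Target is symptom status in all treated: completer rate minus all-treated rate = (r/25) × (pc − pq). The gap is zero if the removed do as well as those kept, and negative if they do better.
- Target counts leaving without an assessment as not controlled: with x controlled, x/(25 − r) − x/25 = x·r / [25(25 − r)]. This is positive at either time point whenever r ≥ 1 and x ≥ 1.

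**Step 3: size with about 70% of completers controlled.** The range runs from none to all of the removed being controlled.

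| Removed | Completer rate | All treated, none of the removed controlled | All treated, all of the removed controlled | Gap (points) |
|---|---|---|---|---|
| 3 | 15/22 = 68.2% | 15/25 = 60.0% | 18/25 = 72.0% | +8.2 to −3.8 |
| 4 | 15/21 = 71.4% | 15/25 = 60.0% | 19/25 = 76.0% | +11.4 to −4.6 |
| 5 | 14/20 = 70.0% | 14/25 = 56.0% | 19/25 = 76.0% | +14.0 to −6.0 |

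With 5 removed and 1 of them controlled, the gap is 70.0 − 15/25 = 70.0 − 60.0 = +10.0. A gap above 10 points at this rate therefore needs 4 or 5 removals with none controlled, or more removals.

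Exact 95% intervals for the first row are 45.1–86.1 (15/22), 38.7–78.9 (15/25) and 50.6–87.9 (18/25).

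**Step 4: the changed-dosage path at 6 months.** Assume 15 patients improved at month 3, with 13 of them controlled at month 6, and 10 did not improve, with 40% controlled at month 6 whether they stay or quit. The all-treated rate is (13 + 4)/25 = 68.0%. If q of the 10 quit, the completer rate is [13 + 0.4(10 − q)]/(25 − q):

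- q = 1: 16.6/24 = 69.2%, gap about +1.2
- q = 3: 15.8/22 = 71.8%, gap about +3.8
- q = 4: 15.4/21 = 73.3%, gap about +5.3

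The outer limits, with whole patients, are:

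- q = 1: 17/24 against 17/25 if the quitter is not controlled (+2.8), or 18/25 if she is (−1.2)
- q = 3: 16/22 against 16/25 if none is controlled (+8.7), or 19/25 if all are (−3.3)
- q = 4: 15/21 against 15/25 if none is controlled (+11.4), or 19/25 if all are (−4.6)

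**Step 5: month 3.** The exit in VI item 1 is for intolerance, and the documents do not link intolerance to symptom response. With pc = 60% and 5 of 25 removed, the gap is +6 points if pq = 30%, 0 if pq = 60% and −4 if pq = 80%. The sign is open.

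**The case against.** **A completer rate may be intended.** Section III speaks of control after 3 and 6 months of medication, which can be read as applying to patients who had that much. On that reading the gap is a difference between two targets, not bias. This stands as a caution: bias has meaning only once a target is named. The plan names none, and the choice moves the reported figure.

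**Removal is inferred.** V.D never says that rejected patients leave the analysis. Figures under V.C and V.D are not shown, and no flow-chart content is visible under VII. This stands too. It is the natural reading, because rejection is listed separately from exit, but it applies to the visible text only.

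**The count is not hidden.** A reader might infer that nobody could tell how many patients a reported rate leaves out. The documents do not support that: IX.1 requires case numbers and percentages, so the denominator can be worked out and compared with the number enrolled. The reasons, and whether the choice followed sight of the outcomes, cannot be recovered.

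**Three-month courses.** A reader might infer that IV creates a planned group who stop at month 3 and have no place in the 6-month rate. VI item 2 describes no such stop, and a three-month minimum is compatible with a six-month course. The relation between the two sections needs clarifying, but no conflict is shown.

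**Sampling error and diary checks.** The interval for 15/22 spans 41 points, far more than any gap shown. That is true, but an interval displays sampling error, whereas an unstated denominator is not displayed. The joint check of E-diary completeness at each interview (VIII.2) should limit poor-data rejections; it does not touch the other routes out.

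**Conclusion.** The point holds for the visible text. Following the rejection, exit and visit rules as written can give completer-type rates at 3 and 6 months, because no denominator is set.

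If the target is symptom status in all treated patients, upward bias is plausible at 6 months and its direction is unknown at 3. A reader might infer that the 6-month rate must be inflated. That goes too far: neither symptom control nor significant improvement is defined in the visible text, so the two cannot be equated, and the direction for rejected patients is unknown. If leaving without an assessment counts as not controlled, the completer rate is higher at both time points whenever such a patient exists and anyone is controlled.

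The size rests wholly on assumed counts at the minimum N: roughly 1 to 5 points on the changed-dosage path when quitters do as well as comparable stayers, and up to +14.0 or −6.0 points with 5 removals. The analysis is descriptive with no success threshold, so no stated decision changes. This is a cheap improvement, held with medium confidence.

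**What to change.** In V.D and IX, state that:

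1. The main denominator at both time points is all patients who took at least one dose.
2. The observed outcome is used wherever a usable assessment exists at that time point, whether or not the patient is still on drug. Only patients with no usable assessment at that time point count as not controlled.
3. The V.D rejection criteria apply only to a secondary per-protocol rate, decided without sight of the outcome.
4. One best-case rate, with missing counted as controlled, is reported beside the main rate. Both have exact 95% intervals, and exits and rejections are listed by reason and time.

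Also clarify how the three-month minimum in IV relates to the course in VI, where item 4 says "the patient can continue this drug therapy after this six-month study". Any patient without a month-6 assessment follows rule 2 and is listed separately.

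**Cost.** A few sentences; the denominator rule needs no extra data. The main rate becomes less favourable and may understate benefit if some unassessed patients were controlled; the best-case rate bounds this. If the sponsor chooses to assess consenting patients at month 6 after they stop drug, each visit brings the pelvic MRI and blood tests in VIII.2, but the rule does not depend on it. No dosing or stopping rule is changed.
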